17.2. DISCONTINUATION DUE TO ANY REASONS

The percentage of subjects who discontinued for any reason (ie, all cause discontinuation). The percentage will be calculated similarly as that of the primary endpoint along with a corresponding 95% CI.

Kaplan-Meier analysis as in section [17.1](#) will be performed for time to discontinuation for any reasons.

17.3. ADVERSE EVENTS AND PRE-TREATMENT EVENTS

Adverse events (AEs) and pre-treatment events will be coded using MedDRA central coding dictionary, Version 22.0 or higher.

Any COVID-19 related Adverse Events and pre-treatment events will be identified using a pre-defined search:

Document:	PPD		
Author:	PPD	Version Number:	1.0

Table 2: Predefined search criteria for COVID-19 related adverse events or pre-treatment events.

Lower Level Term	Lower Level Term Code	Preferred Term	Preferred Term Code	Search Criteria for COVID-19 Related Adverse Events or Pre-treatment Events
Coronavirus test positive	1007025	Coronavirus test positive	10070255	Preferred Term Code = 10070255 or 10053983
Coronavirus infection	10051905	Corona virus infection	10053983	

AEs are defined as untoward medical occurrences that started at the same time of or after the first dose of study drug. Untoward medical occurrences that started prior to the first dose of study drug are pre-treatment events.

Whenever available, the time information should be accounted for in the derivation of AEs vs. pre-treatment events. In the case where time is not available, untoward medical occurrences that started on or after the day of the first dose of study drug will be considered AEs; those that started before the day of the first dose of study drug will be considered pre-treatment events.

See [APPENDIX 2](#) for handling of partial dates for AEs. In the case where it is unclear whether an untoward medical occurrence is an AE or a pre-treatment event, the algorithm uses a conservative approach where the untoward medical occurrence is classified by the worst case; i.e., AE.

AEs (including serious adverse events (SAEs)) are collected into the clinical database until the last study visit. For subjects who do not roll over to study 361-309, the last study visit will be Visit 11 (the follow-up visit) which per protocol should occur 7 (\pm 2) days after the last dose of study drug. For subjects continuing into study 361-309, the last 361-308 study visit will be Visit 10 (the end of treatment visit). If an AE (or a pre-treatment event) started in 361-308 and was ongoing at rollover, this adverse event (pre-treatment event) will be marked Ongoing in the 361-308 database. It will also be re-entered into the 361-309 database and its outcome will be monitored and updated in the 361-309 database.

Overall summary of the incidence of all AEs, AEs related to COVID-19, study medication-related AEs, severe AEs, serious AEs, AEs leading to discontinuation from study, AEs leading to study medication withdrawal, AEs leading to study medication interruption, and AEs leading to death will be provided by treatment group. This overall incidence summary will also be separately presented for the following subgroups: country, sex, age group, number of prior hospitalizations for treatment of schizophrenia, duration of schizophrenia, and BMI category.

Listings will be provided for all AEs, AEs related to COVID-19, study medication-related AEs, severe AEs, serious AEs, AEs leading to discontinuation from the study, AEs leading to study medication withdrawal, AEs leading to study medication interruption, AEs leading to death, AEs of potential drug abuse and dependence and extrapyramidal AEs. A listing of the pre-treatment events will also be presented. When complete event start date and complete event end date are available, duration of AEs/pre-treatment events will be calculated as: event end date – event start date + 1. Duration will be presented in data listings.

Document: PPD

Author: PPD

Version Number:

1.0

Version Date:

06MAY2024

For all summaries, each subject will be counted only once within each category (e.g., an AE type, a severity level, a relationship category, a SOC, a high level term (HLT), and a PT). If not otherwise specified, all summaries will present the number and percentage of subjects as well as the number of events. For summaries by SOC and PT, AEs will be sorted by SOC based on the internationally agreed order (see [APPENDIX 4](#)) and then by PT in decreasing frequency in the “SEP-363856 50 to 100 mg/day” column. For summaries by SOC, HLT, and PT, AEs will be sorted by SOC based on the internationally agreed order and then by HLT and PT in decreasing frequency in the “SEP-363856 50 to 100 mg/day” column.

COVID-19 related pre-treatment events related pre-treatment events and AEs will be displayed similarly as any other pre-treatment events and AEs.

Document:

PPD

Author:

PPD

Version Number:

1.0

Version Date:

06MAY2024

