Informed consent will be obtained from each subject before any study procedures are performed. Subjects will be evaluated for eligibility during a Screening Period of up to 21 days, during which they will continue on their pre-switch antipsychotic medication while being tapered off any prohibited medications ([Section 10.3.2](#)) in a manner that is consistent with labeling recommendations and conventional medical practices. Non-prohibited psychotropic medications other than the pre-switch antipsychotic may be continued during the study but must have been stable for at least 6 weeks prior to Screening and should be maintained at a stable dose and regimen (see [Section 10.3.1](#)).

Subjects who are being treated with two antipsychotic medications will be permitted to enter the Screening Period. At the start of Screening, the Investigator will determine which antipsychotic medication is considered “primary”, and the other one will be tapered off during the Screening Period.

Subjects who screen fail may be re-screened twice, if judged appropriate by the Investigator after discussion with the Medical Monitor. Re-screened subjects will be re-consented, assigned a new subject number, and all Visit 1 procedures will be repeated.

Open-label Treatment Period (8 weeks):

At Baseline (Day 1) (pre-switch [PS] Baseline), subjects who have successfully completed Screening and have met the eligibility criteria will begin open-label treatment with SEP-363856 while continuing to take the full dose of their pre-switch antipsychotic. SEP-363856 dosing will begin the evening of the PS Baseline visit and will continue once-daily, in the evening at bedtime, for the remainder of the Treatment Period, during which the procedures outlined in [Table 2](#) will be conducted. Subjects will be evaluated at PS Baseline and weekly throughout the rest of the study. [Section 10.3](#) describes the circumstances and specifications for which prior and concomitant psychotropic medications other than the pre-switch antipsychotic are allowed in this study.

Subjects will receive SEP-363856 50 mg/day from Day 1 through Day 3 and 75 mg/day from Day 4 through Day 7. Every effort should be made to maintain subjects at 75 mg/day from Day 4 through Day 7. Beginning on Day 8, the dose of SEP-363856 can be adjusted in increments of 25 mg among 3 dose levels (50, 75 and 100 mg), according to the following requirements:

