12. SAFETY REPORTING

12.1. Definitions

12.1.1. Adverse Events

An adverse event (AE) is any untoward medical occurrence associated with the use of a drug in humans, whether or not considered drug related.

Untoward medical occurrences that occur between the time of signing the informed consent form (ICF) and first drug administration are pre-treatment events. Those that occur after first administration of study drug are considered AEs.

An AE can, therefore, be any unfavorable and unintended sign (including an abnormal laboratory finding), symptom, or disease occurring after the administration of a medicinal (investigational) product, whether or not considered related to the medicinal (investigational) product. AEs may include the onset of new illness and the exacerbation of pre-existing conditions. AEs will be collected from the signing of the ICF to the last study visit (including Follow-up Visit for those not enrolling in open-label extension).

The Investigator should attempt to establish a diagnosis of the event based on signs, symptoms, and/or other clinical information. In such cases, the diagnosis should be documented as the AE and not the individual signs/symptoms.

If a subject answers "yes" to "Suicidal Ideation" Item 4 (active suicidal ideation with some intent to act, without specific plan) or Item 5 (active suicidal ideation with specific plan and intent) on any post-Baseline C-SSRS assessment, an associated AE must be reported.

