12.1.2. Serious Adverse Events

A serious adverse event (SAE) is an AE that meets one or more of the following criteria:

- Results in death.
- Is life-threatening.
- Requires hospitalization or prolongation of existing hospitalization.
- Results in persistent or significant disability or incapacity.
- Is a congenital anomaly or birth defect.
- Is an important medical event that may jeopardize the subject or may require a medical or surgical intervention to prevent one of the outcomes listed above.

Examples of such medical events include allergic bronchospasm requiring intensive treatment in an emergency room or at home, blood dyscrasias or convulsions that do not result in inpatient hospitalization.

The term "severe" is often used to describe the severity of a specific event (as in mild, moderate, or severe myocardial infarction) (see [Section 12.3](#)); the event itself, however, may be of relatively minor medical significance (such as severe headache). This is not the same as "serious," which is based on subject/event outcome or action criteria usually associated with events that pose a threat to a subject's life or functioning as defined by the criteria above.

During the study, if a subject has a hospitalization or procedure (eg, elective surgery) that was scheduled before the study entry, ie, before informed consent for an event/condition that occurred before the study, the hospitalization is considered a therapeutic intervention and not the result of a SAE. However, if the event/condition worsens during the study, it should be reported as an AE (or SAE, if the event/condition results in a serious outcome such as prolongation of hospitalization).

Life-threatening means that the subject was, in the view of the Investigator, at immediate risk of death from the event as it occurred. This definition does not include an event that had it occurred in a more severe form might have caused death.

SAE criteria information will be captured on the CRF.

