17.1. DISCONTINUATION DUE TO CLINICAL REASONS

Discontinuation for clinical reasons is defined as reasons due to AE or lack of efficacy. AE will follow the definition as in section [17.3](#).

The percentage of subjects who discontinued for clinical reasons will be calculated by a proportion consisting of the number of subjects who experience a discontinuation event due to clinical reasons as the numerator divided by the number of subjects in the safety population as the denominator multiplied by 100 along with a corresponding 95% confidence interval (CI).

The number and percentage of subjects, who discontinued early from the open-label treatment period (including both clinical reasons, ie, discontinued due to an AE or lack of efficacy (primary endpoint) and any reason for discontinuation (secondary endpoint)) will be presented.

The time-to-discontinuation for clinical reasons will be summarized descriptively, (eg, n, median, 25th percentile, 75th percentile, minimum and maximum, and 95% CI on median, where possible).

Time to discontinuation for clinical reasons since first dose of study medication will be plotted using Kaplan-Meier curves for the safety population by treatment group. Probability of remaining on treatment at Day 56, median time to discontinuation, and their 95% confidence intervals will be estimated using the Kaplan-Meier method for the safety population by treatment group.

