APPENDIX 2. PARTIAL DATE CONVENTIONS

The actual dates as collected on the CRF will be presented in the listings. Imputed dates will not be presented in the listings unless otherwise specified.

ALGORITHM FOR ADVERSE EVENTS

As a general rule, if the start date of an AE is available and the start time of the AE is not available, the AE will be considered to have started after the study drug dose administered on the day of the AE start date.

In case of partial or missing AE start and/or end dates, impute partial or missing event start and/or end dates (if not ongoing) using the algorithm below. If an AE has some missing components in both the start and end dates, first impute the end date.

AE end date imputation

- If year and month (YYYY-MM) of AE end date are known, then impute the missing day to be the earlier of (last day of the month; date of last contact).
- If only year (YYYY) of AE end date is known, then impute the missing month and day to be the earlier of (31st December; date of last contact).
- If AE end date is completely missing and AE is not ongoing, then impute AE end date to be date of last contact.

AE start date imputation

- If year and month (YYYY-MM) of AE start date are known and YYYY-MM = year and month of 361-30 study med start date, then impute AE start date to be the earlier of (361-308 study med start date; full or imputed AE end date [if non-missing]).
- If year and month (YYYY-MM) of AE start date are known and YYYY-MM ≠ year and month of 361-308 study med start date, then impute AE start date to be YYYY-MM-01.
- If only year (YYYY) of AE start date is known and YYYY = year of 361-308 study med start date, then impute AE start date to be the earlier of (361-308 study med start date; full or imputed AE end date [if non-missing]).
- If only year (YYYY) of AE start date is known and YYYY ≠ year of 361-308 study med start date, then impute AE start date to be YYYY-01-01.

Document: PPD

Author: PPD

Version Number:

1.0

Version Date:

06MAY2024

- If AE start date is completely missing, then impute AE start date to be the earlier of (361-308 study med start date; full or imputed AE end date [if non-missing]).

Using the full or imputed event dates, assign events into pre-treatment events vs. AE as described below.

If both event start date/time and 361-308 study med start date/time are available:

- If event start date/time < 361-308 study med start date/time, then pre-treatment event.

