- If event start date/time \geq 361-308 study med start date/time, then AE.

If (event start date is available and time is not available) and/or (361-308 study med start date is available and time is not available):

- If event start date < 361-308 study med start date, then pre-treatment event.
- If event start date \geq 361-308 study med start date, then AE.

Document: PPD

Author: PPD

Version Number:

1.0

Version Date:

06MAY2024

ALGORITHM FOR PRIOR / CONCOMITANT / POST-TREATMENT MEDICATIONS

In case of partial or missing medication start and/or stop dates, impute the partial or missing dates using the algorithm below.

If a medication has some missing components in both the start and stop dates, first impute the stop date.

Impute stop date as latest possible date

- If only day unknown, impute to the earlier of (last day of the month; date of 361-308 last contact).
- If month and day unknown, impute to the earlier of (31st December; date of 361-308 last contact).
- If stop date is completely unknown and medication is not ongoing, impute to date of 361-308 last contact.

Impute start date as earliest possible date

CRF questions: 'Started prior to first dose?' = Yes; 'Started after last dose of study medication?' = No.

- If only day unknown, impute to the later of (first day of the month; date of birth [if full date is available]).
- If month and day unknown, impute to the later of (1st January; date of birth [if full date is available]).
- If start date is completely unknown, impute to the earlier of (date of informed consent*; full or imputed medication stop date [if not missing]).

CRF questions: 'Started prior to first dose?' = No; 'Started after last dose of study medication?' = Yes.

- If only day unknown, impute to the later of (first day of the month; 361-308 study med end date + 1).
- If month and day unknown, impute to the later of (1st January; 361-308 study med end date + 1).
- If start date is completely unknown, impute to 361-308 study med end date + 1.

CRF questions: 'Started prior to first dose?' = No; 'Started after last dose of study medication?' = No.

- If only day unknown, impute to the later of (first day of the month; 361-308 study med start date).
- If month and day unknown, impute to the later of (1st January; 361-308 study med start date).
- If start date is completely unknown, impute to 361-308 study med start date.

Document: PPD

Author: PPD

Version Number:

1.0

Version Date:

06MAY2024

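### The SAP separates AEs from pre-treatment events by start date alone, so a Screening event that worsens on study drug can go uncounted, and SAP 17.1 read literally carries the gap into the primary endpoint

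*SAP*

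**What the plan says.** **SAP.** Section 17.3 gives a pair of definitions. The first is "AEs are defined as untoward medical occurrences that started at the same time of or after the first dose of study drug". The second is "Untoward medical occurrences that started prior to the first dose of study drug are pre-treatment events". Appendix 2 turns them into code: "If event start date/time < 361-308 study med start date/time, then pre-treatment event", or, where a time is missing, "If event start date < 361-308 study med start date, then pre-treatment event". Pre-treatment events are listed. The summaries of AEs leading to discontinuation (17.3.4), AEs leading to study medication withdrawal (17.3.5), SAEs (17.3.7) and AEs leading to death (17.3.8) each start from events already classed as AEs. For the primary endpoint, section 17.1 says "AE will follow the definition as in section" 17.3. Section 3.7 declares no change to analysis from the protocol.

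**Protocol.** Section 12.1.1 also splits events at the first dose, but adds: "AEs may include the onset of new illness and the exacerbation of pre-existing conditions". Section 12.2 and sections 11.4.2 to 11.4.5 make clinically significant changes from Screening in laboratory tests, vital signs, ECG and examinations AEs. Section 12.1.2 says "if the event/condition worsens during the study, it should be reported as an AE", but only about hospitalizations or procedures scheduled before consent. Section 12.3 has the AE or pre-treatment label assigned by program, not by the site. Section 13.1 records the discontinuation reason on the CRF, with Adverse event and Lack of efficacy as separate options and no condition on when the event began.

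**The concern.** The design makes events with a Screening onset plausible. During Screening, subjects stay on the pre-switch antipsychotic "while being tapered off any prohibited medications" (Protocol 7.1). A second antipsychotic is also withdrawn then, and hypnotics are to be tapered before SEP-363856 starts (Protocol 10.3.1). Insomnia or anxiety could begin at that point and worsen on study drug.

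If the worsening stays on the Screening-dated record, the event fails the first filter of every AE table, even when that record is marked as serious or as the cause of discontinuation.

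The AE route into the primary numerator matters most for worsening. Protocol 13.1 reserves Lack of efficacy for subjects whose condition has neither worsened nor improved significantly, so a subject who stops because of worsening would ordinarily enter as an Adverse event discontinuation. That is the route SAP 17.1 ties to the start-date rule. Any omission lowers the AE counts and the primary percentage; none can raise them.

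**Working it through.** **1. Follow one event through the rules.** Take a symptom that begins in Screening, is ongoing at the first dose and worsens in Week 2.

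| How the site records the worsening | Class under SAP 17.3 and Appendix 2 | AE tables |
|---|---|---|
| New record, start date in Week 2 | AE | Counted |
| Existing record updated, start date still in Screening | Pre-treatment event | Not counted; listing only |

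Neither document says which row applies to an ongoing symptom. The protocol's AE requirement for changes from Screening covers objective and examination findings. The SAP's worst-case rule, which defaults to AE, covers unclear timing, so it does not help when the Screening date is known.

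**2. Follow the same subject into the primary endpoint.** Suppose the subject discontinues with CRF reason Adverse event.

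- If the numerator is built from the CRF reason, the subject counts in both rows.
- If it is built from AE records meeting 17.3, as 17.1 literally says, the subject does not count in the second row.

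The SAP does not name the source.

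**3. Reproduce the plan's precision figures.** Half width = 1.96 × √(p(1 − p)/n).

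- Original plan (Protocol 15.1): p = 0.15, n = 120 gives 6.39 points; stated 6.4.
- Revised plan (SAP 3.4): p = 0.072, n = 100 gives 5.07 points; stated 5.1.

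Both reproduce, and this point does not affect them.

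**4. Size per subject.** Inputs: 101 enrolled and a rate of about 7.2% (both SAP 3.4). Assumption: all 101 were dosed, so the safety population is 101.

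- One subject: 1/101 = 0.99 percentage points.
- Expected numerator: 0.072 × 101 = 7.3, taken as 7.
- If the true count is 7 and one is lost: 7/101 = 6.93% becomes 6/101 = 5.94%, a loss of one seventh of the numerator.
- If 7 are counted and some were already lost, restoring them gives:

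| Numerator | Percentage | Wald 95% CI | Clopper-Pearson 95% CI |
|---|---|---|---|
| 7 | 6.93 | 1.98 to 11.88 | 2.83 to 13.76 |
| 8 | 7.92 | 2.65 to 13.19 | 3.48 to 15.01 |
| 9 | 8.91 | 3.35 to 14.47 | 4.16 to 16.24 |

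The range of 0 to 2 restored subjects is an assumption. The documents give no count.

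**The case against.** A reader might infer that every Screening event that worsens on drug automatically leaves the AE tables and the primary numerator, and that the result is therefore biased. The documents do not support that, for four reasons.

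- **Recording.** Protocol 12.1.1 lets an exacerbation be an AE in its own right, and objective or examination changes from Screening must be recorded as AEs. Entered with a post-dose start date, they meet SAP 17.3. CRF completion instructions, which might settle the matter for symptoms, are not among the documents.
- **Numerator source.** Much of the plan points to the CRF reason. Protocol 13.1 records it, SAP 9 tabulates it, SAP 7.5 has a subgroup for the reason for clinical discontinuation, and SAP 3.7 declares no departure from the protocol. Nothing explicitly tells the programmer to delete a subject because the linked event began before Day 1.
- **Origin of the rule.** The split at first dose, and doing it by program, come from the protocol.
- **Population.** Exclusion 4 bars subjects with a clinically significant change in symptom status between Screening and Baseline, and inclusions 6 to 8 require limited severity and stability. Psychotic worsening that starts in Screening is therefore largely screened out. Insomnia and anxiety are better examples.

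All four stand, and they limit the claim. They do not remove it. No text requires a new record for an ongoing symptom, and the only sentence in 17.1 that says what counts as an AE points to 17.3. The subject also remains in the all-cause secondary endpoint and the event in a listing, which limits the harm without correcting the primary count.

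**Conclusion.** The gap is real but conditional. SAP 17.3 and Appendix 2 state a rule that can undercount worsening and newly serious events when the worsening is kept on a Screening-dated record. On a literal reading of 17.1, the same rule can remove an Adverse event discontinuation from the primary numerator, which is at odds with Protocol 12.1.1 and 13.1.

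Each affected subject is worth 0.99 points, assuming a safety population of 101. That is small against a half width of about 5 points but about one seventh of an expected numerator of 7. The number affected is unknown and may be zero, so this is not a demonstrated bias. The direction is certain: any error favours the switch. A primary endpoint should not rest on an unstated CRF convention and an unnamed data source, so it is worth settling before lock.

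**What to change.** 1. **SAP 17.3 and Appendix 2.** Also class as an AE any event that starts before the first dose and increases in severity or becomes serious at or after it, dated at the worsening. Action on study drug should not be a trigger by itself, because it would turn an unchanged pre-existing event into an AE.
2. **SAP 17.1.** Replace the cross-reference to 17.3 with: all safety-population subjects whose CRF discontinuation reason is Adverse event or Lack of efficacy, whatever the start date of the linked event.
3. **Before lock.** Reconcile Adverse event discontinuations against events classed as pre-treatment, and query ongoing pre-treatment events for a worsening date.

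The cost is a few SAP sentences, one programming flag and a short data query. The query is needed because the AE attributes listed in Protocol 12.3 do not include a worsening date. The rates may become slightly less favourable. If no subject is affected, the results do not change and the ambiguity is gone.
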